### **Definition of a Metabolic Response in FDG-PET**

Based on the reproducibility of the FDG-signal in untreated tumors, relative changes of approximately 20% are very unlikely to be due to measurement errors or spontaneous fluctuations of tumor metabolic activity (72,73). These data establish the minimal effect of treatment on tumor metabolic activity that can be assessed by FDG-PET. However, a measurable change in metabolic activity does not necessarily imply that treatment has a beneficial effect for the patient. A recent study evaluated the prognostic implications of a measurable change in tumor glucose utilization in patients with advanced NSCLC, who were treated with palliative platinum-based chemotherapy. A "metabolic response" in PET was prospectively defined as decrease of the SUV of the primary tumor by at least 20%. A total of 57 patients were included in the study and 28 tumors showed a metabolic response after the first chemotherapy cycle. Median progression-free survival of metabolic nonresponders was only 1.8 months versus 5.9 months for metabolic responders. Median overall survival of metabolic responders was 8.4 months and only 5.0 months for metabolic nonresponders (65). The sensitivity and specificity of a metabolic response for prediction of best response according to RECIST criteria were 95% and 74%, respectively.

These data indicate that a measurable change in tumor FDG uptake after the first cycle of chemotherapy is associated with a palliative effect of therapy. These data and the data on the test-retest reproducibility of FDG-PET suggest that a 20% decrease in tumor FDG uptake may be

used to define a metabolic response in patients with NSCLC. However, we will use slightly stricter criteria for a metabolic response in the present study and define a metabolic response as a decrease of tumor FDG uptake by 25%. The rationale for this definition is that the test/retest reproducibility of FDG-PET in a multicenter trial may be lower than previously reported in single-center studies. Therefore, a 20% threshold may not be robust enough for a multicenter trial. Defining a metabolic response as a 25% decrease of tumor FDG uptake makes this study also consistent with previous recommendations by the EORTC (74).

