Although data in the literature support the use of a 25% decrease in tumor FDG uptake as a criterion for a metabolic response, we cannot exclude that other threshold values may allow a better prediction of patient outcome. Therefore, receiver operating characteristic (ROC) curves will be calculated for prediction of best response by quantitative changes in FDG uptake after one and two cycles of chemotherapy. Predictive accuracy will be evaluated through 95% confidence intervals for the area under the ROC curve (75)

All PET/CT data will follow the guidelines specified in appendices B and C (76) .

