- 4) Profile the genomes of each cell population using oligonucleotide CGH arrays. This will confirm the identification of tumor populations in each sample and provide genomic landmarks

for NGS analysis.

5) Perform whole exome analysis of the sorted tumor population and matching germ line sample for each of the patients. The combined aCGH and exome data will be mined to identify genes and pathways that are targeted by select somatic events in each of the patient subsets

6) To assess stable disease duration (SDD).

7) To assess the association between response to vorinostat treatment and HR23B on tumor paraffin blocks.

Exploratory Objective 1 concerns the potential association of PET/CT response (magnitude of decrease in SUV after 1 treatment cycle) with clinical response by RECIST 1.1 criteria. Percent change in SUV ( $\Delta$ SUV) is a continuous variable, whereas objective response is a categorical (typically, binary) variable. First, we will use receiver operator characteristic (ROC) curve analysis to determine the optimal cutoff in the distribution of  $\Delta$ SUV, in relationship to objective response (yes/no). That will allow us to define “PET response”. We will also compare the descriptive statistics of the  $\Delta$ SUV distribution in the RECIST responders vs non-responders. At Stage 1 (n=12), the association of  $\Delta$ SUV with subsequent best tumor response will be explored in a simple 2 x 2 contingency table, with point and 90% CI estimates of objective response rates among the patients with vs. without PET response. Descriptively only, we can then examine the point and CI estimates to see if there is a hint of any association. At Stage 2 (n=29), we would repeat the same descriptive, exploratory investigation, and then determine what, if any, additional statistical analysis might be appropriate. For example, that might involve exact logistic regression to model the log-odds of later objective response as a function of only one predictor: early PET response (yes/no). This exact logistic modeling investigation would still be viewed as exploratory only, but would yield a point and 90% CI estimate of the odds ratio for response.

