Exploratory Objective 2 concerns the potential association of PET/CT response (magnitude of decrease in SUV after 1 treatment cycle) with censored PFS. “PET response” (yes/no) will be determined as just described above for Exploratory Objective 1. At Stage 1 (n=12), to explore the potential association of PET/CT response with length of censored PFS, we will use the Cox proportional hazards model. This analysis will focus on the length of PFS after the second PET/CT scan, and will be exploratory only. The goal would be to determine if there is any hint of a potential positive association in the hypothesized *direction*, i.e., is the hazard ratio (HR) < 1 or not for patients with an early PET/CT response. At Stage 2 (n=29), we would repeat the same Cox model investigation, but pay more attention to the magnitude of (HR), its precision (i.e., half-width of its 90% CI), but not its statistical significance (i.e., p-value). Again, this Cox modeling investigation would still be viewed as exploratory only. A similar analysis will be performed utilizing the third PET/CT scan, taken after 2 treatment cycles, at day 56.

Exploratory Objectives 3, 4 and 5 are strictly exploratory and will be reported as descriptive results

Exploratory Objective 6 concerns yet another time-to-event endpoint (SDD), which is defined in [Section 10.1.5](#). The analysis of the censored SDD distribution will use the same approach as described above for [Secondary Objectives 3-5](#).

Exploratory Objective 7 concerns a biomarker (HR23B), measured by immunohistochemistry (IHC). Its expression level will be recorded as: 0, 1+, 2+, or 3+. In light of the small to modest sample sizes for this Phase II trial (either n=12 after Stage 1, or n=29 after Stage 2), we will dichotomize the total staining score (TSS) of HR23B into  $\geq 6$  (“positive”) or  $< 6$  (“negative”).

At Stage 1 (n=12), the association of HR23B’s dichotomized expression level (absence/presence) to objective response (yes/no) can be explored via a simple 2 x 2 contingency table. From the table we can compute the point and 90% CI estimates of response rates among the patients who do vs. those who do not “express” HR23B. The most basic exploratory observation will be the *direction* of the association, i.e., whether the point-estimate of response rate is higher (or lower) among expressers of HR23B. We can also observe the precision in the estimate of the response rate via its CI.

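### The Cox model of early PET change and PFS uses percent change in SUV only as yes/no, which under stated assumptions widens the 90% CI by about 25–36%

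*Combined protocol and SAP*

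**What the plan says.** Section 12.4, under Exploratory Objective 1, notes that percent change in SUV "is a continuous variable, whereas objective response is a categorical (typically, binary) variable". It then turns the change into a category: "First, we will use receiver operator characteristic (ROC) curve analysis to determine the optimal cutoff in the distribution of" SUV change, judged against RECIST response, and that cut defines PET response.

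Under Exploratory Objective 2 the same yes/no variable is carried into the analysis of PFS: "to explore the potential association of PET/CT response with length of censored PFS, we will use the Cox proportional hazards model". The follow-up time is PFS after the scan. At Stage 1 (12 patients) the question is "is the hazard ratio (HR) < 1 or not for patients with an early PET/CT response". At Stage 2 (29 patients) the plan looks at the size of the hazard ratio and the half-width of its 90% CI, and expressly sets the p-value aside. A similar analysis is planned for the day 56 scan. No Cox model with SUV change as a continuous covariate appears anywhere.

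Section 2.3 gives a fixed definition, saying the study will "define a metabolic response as a decrease of tumor FDG uptake by 25" percent, and then adds that "we cannot exclude that other threshold values may allow a better prediction of patient outcome". It also says that very few data exist on PET for monitoring response in this disease. The Schema makes the PET/CT scans optional and dependent on funding.

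**The concern.** A Cox model does not need a cut-point, and the documents do not establish one for adenoid cystic carcinoma. Reducing a graded measurement to two groups treats a patient just past the cut the same as one with a very large fall in uptake. It also treats a patient just short of the cut as having no response. If the hazard changes gradually with SUV change, that within-group information is lost.

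The loss occurs whichever cut is used, the fixed 25% fall or the ROC-derived one, so the point does not depend on how the cut is chosen. What is at stake is the precision of one exploratory estimate from at most 29 patients, and possibly fewer because the scans are optional. The split may also leave one PET group with very few patients.

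**Working it through.** **1. The plan's own figure.** The cap of 29 comes from the Simon design in section 12.1.1: 5% versus 20%, continue with at least 1 response in 12, promising with at least 3 in 29. Exact binomial calculation gives early termination 0.95^12 = 0.540, alpha 0.148 and power 0.9005. These agree with the stated 0.540, 0.15 and 0.90. The plan states no hazard ratio, event count, responder share or precision target for the PET–PFS model, so there is nothing further to reproduce.

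**2. Inputs.**
- Maximum sample: 29 (section 12.1.1).
- Criterion at Stage 2: hazard ratio size and 90% CI half-width (section 12.4).
- Share of PET responders: not given for this trial. The only share in the documents is 28/57 = 49%, from the NSCLC study in section 2.3, which used a 20% cut.
- Assumed: SUV change roughly normal, effect linear on the log hazard, responder share 25–50% (more uneven splits also shown).

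**3. Formula.** Let x be SUV change in SD units, D the number of events and p the share of PET responders.
- Continuous model: SE of the log hazard ratio per SD ≈ 1/√D.
- Yes/no model: SE ≈ 1/√(D·p(1−p)), and the two groups differ in mean x by φ(z_p)/(p(1−p)).
- Dividing the second SE by that difference puts both models on the per-SD scale. The efficiency of the split is then φ(z_p)²/(p(1−p)), and the CI is wider by the factor 1/√efficiency.

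At p = 0.50: 0.3989²/0.25 = 0.637, factor 1.25. At p = 0.25: 0.3178²/0.1875 = 0.539, factor 1.36.

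| PET responders | Efficiency | Information lost | CI width factor | 29 events count as |
|---|---|---|---|---|
| 50% | 0.637 | 36.3% | 1.25 | 18.5 |
| 49% (NSCLC share) | 0.636 | 36.4% | 1.25 | 18.4 |
| 25% | 0.539 | 46.1% | 1.36 | 15.6 |
| 15% | 0.426 | 57% | 1.53 | 12.4 |
| 10% | 0.342 | 65.8% | 1.71 | 9.9 |

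**4. On the plan's scale.** With 29 events, the most the sample allows, the 90% half-width for the log hazard ratio per SD is 1.645/√29 = 0.305 in the continuous model. For the split it is 0.305 × 1.253 = 0.383 at 50% responders and 0.305 × 1.363 = 0.416 at 25%. With 20 events the three figures are 0.368, 0.461 and 0.501.

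**5. Stage 1.** Here the plan reads only direction. For an effect size, take the NSCLC medians in section 2.3 (1.8 and 5.9 months). With exponential PFS the hazard ratio is 1.8/5.9 = 0.305, or about 0.75 on the log scale per SD. Assume 9 events in 12 patients. The chance of a correct direction is Φ(√9 × 0.75) = Φ(2.25) = 0.988 for the continuous model. It is Φ(2.25 × 0.798) = 0.964 for a 50/50 split and Φ(2.25 × 0.734) = 0.951 for 25/75. The loss is about 2–4 points, so the cost falls mainly on precision at Stage 2.

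**The case against.** The strongest reply has three parts.

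- **The yes/no variable is what the objective names.** Section 1.3 asks about metabolic response and PFS. Section 2.3 supports a response category with test–retest reproducibility, NSCLC outcome data and an earlier EORTC recommendation. On this view, a hazard ratio per 10-point fall answers a different question. This stands as a reason to keep the yes/no result. It does not justify having nothing else, because section 12.4 itself explains PET/CT response under Objective 2 as the magnitude of the SUV decrease.
- **The size of the loss rests on assumptions.** The documents contain no SUV distribution, event count or responder share for this disease. If the true effect is a step at the cut, the yes/no model loses little and may do better. This is correct and limits the claim.
- **Little depends on it.** The analysis is exploratory, the scans are optional, and no primary, secondary or safety conclusion uses it. This also stands, and it sets the weight of the point.

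A reader might infer that the analysis of response (Objective 1) has the same gap. The documents do not support that. Section 2.3 plans ROC curves for best response from quantitative FDG change after one and two cycles, with 95% CIs for the area under the curve. That is a full-scale, rank-based analysis with an interval. The exact logistic model in section 12.4 is offered only as an example of what might be done.

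**Conclusion.** The point holds for Exploratory Objective 2. Percent change in SUV enters the Cox model for PFS only as yes/no at both scans, and the plan gives no reason for leaving out the continuous form. With roughly normal SUV change, a log-linear effect and 25–50% PET responders, the split discards about 36–46% of the information and widens the 90% CI on the equivalent effect by about 25–36%. This range is not an upper limit: at 10% responders the loss is about 66%. It shrinks or reverses under a true step effect at the cut.

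A reader might go further and attach a definite loss of power at 29 patients. The documents do not support a single figure. The plan sets the p-value aside and gives none of the inputs a power calculation needs. At a two-sided 5% level the closed form with 29 events gives losses from about 2 to 26 points, depending on effect size and split. Simulation at n = 29 gives about 5 to 31. With the NSCLC effect and split, the closed form gives 8.8 points at 29 events and 15.8 at 20. CI width is the better measure because it is the one the plan says it will read.

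This is a low-cost improvement to an exploratory analysis and does not threaten the trial's conclusions.

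**What to change.** In section 12.4, Exploratory Objective 2, add percent change in SUV as a continuous covariate in the Cox model of PFS after the scan, for both the day 28 and the day 56 scans. Report the hazard ratio per 10-point fall with its 90% CI, and read it as the main measure of association and precision. Keep the yes/no PET response hazard ratio beside it, for comparison with the literature and as a check on log-linearity. Objective 1 needs no change on this account.

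The cost is a sentence or two in the plan and one more exploratory model per scan, with no new data or patients. The downside is the assumption of approximate log-linearity, which the retained yes/no result helps to check.

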At Stage 2 (n=29), we would repeat the same descriptive, exploratory investigation, and then determine what, if any, additional statistical analysis might be appropriate. For example, that might involve exact logistic regression to model the log-odds of later objective response as a function “expression” of HR23B (yes/no). This exact logistic modeling investigation would still be viewed as exploratory only, but would yield a point and 90% CI estimate of the odds ratio for response.

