NGS Analyses Workflow: Once exome sequencing data is generated, we will leverage our substantial bioinformatics and statistics skills, experience, and large-scale computational capabilities to carry out research-objective-specific customized data-analyses. We have several automated workflows that consist of both published and internally developed data analyses tools for processing sequenced data to generate interpretation-ready results. This includes germline results, such as detecting variants, comparisons with a variety of publically available variants datasets (e.g., dbSNP, 1000 genomes, etc.), functional annotation, Ti/Tv ratios, target sequencing efficiency, etc. Further, when both tumor and normal sequencing data is available, we have well-tested sophisticated workflows for somatic variant detection with detailed comparisons with publically available datasets (e.g., COSMIC). Both germline and somatic variants are comprehensively annotated for functional consequences, such as non-synonymous mutations,

frame-shift insertion-deletions. Our workflows are compatible with standard, platform-independent input sequencing data format (e.g., FASTQ format), generate detailed QC and several additional statistical metrics at various stages of data processing, and deliver results that conform to standard output formats, such as BAM (alignments), VCF (variant calls), functional annotation, etc.

HR23B protein levels will be measured by immunohistochemistry (IHC) using published protocols (86). We will use a single thin section slide for all IHC experiments. All assays will be done through TGen's Macromolecular Analyte and Processing Center (MAPC) pending additional funding. In addition a second slide from each patient will be used for further validation of the recurring t(6:9) MYB-NFIB translocation using conventional fluorescent in situ hybridization (FISH) (87). A semiquantitative analysis based upon intensity and frequency of HR23B staining and the type of dermal and epidermal infiltrate will be performed on each biopsy(87). A total staining score (TSS) will be determined out of 13, where a score of greater than or equal to 6 will be considered to be strong HR23B staining. The threshold for differentiating between positive and negative immunostaining will be set at at TSS of equal or higher than 6. This optimal cutoff was determined by the receiver operating characteristic curve (ROC) distribution analysis.

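### Small sample size is not a valid reason to reduce the HR23B staining score to positive/negative; report the full score beside the ≥6 table

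*Combined protocol and SAP*

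**What the plan says.** Section 12.4 (Exploratory Objective 7) cuts the staining score at 6: a value of 6 or more counts as positive and a lower value as negative. The only reason that section gives is "In light of the small to modest sample sizes for this Phase II trial". The samples it has in mind are 12 patients at the first stage and 29 at the second.

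At Stage 1 the plan is a 2 × 2 table of HR23B status by objective response, with response rates and 90% intervals. The main observation is which way the association points. At Stage 2 the description is repeated. A further analysis may follow, for example "exact logistic regression to model the log-odds of later objective response" on HR23B yes/no, giving an odds ratio with a 90% interval.

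Appendix D describes the score itself: "A total staining score (TSS) will be determined out of 13". It sets positivity at 6 or more and adds: "This optimal cutoff was determined by the receiver operating characteristic curve (ROC) distribution analysis". Section 12.4 also says of HR23B: "Its expression level will be recorded as: 0, 1+, 2+, or 3" (the top grade is 3+). That is a different scale from a score out of 13.

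**The concern.** The stated reason runs the wrong way. With few patients, and fewer responders, each observation has to carry as much information as it can. A two-level split discards all ordering within each half. It also leaves an exact analysis with very few attainable results. Exact logistic regression accepts the full score as its single predictor at the same sample size, so the small sample does not force the split.

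What is at stake is the precision of one exploratory biomarker result. If all responders fall on one side of the cut, the planned odds ratio has no finite limit on one side and the reader learns little. By contrast, Objective 1 compares the full distribution of change in SUV between responders and non-responders. Objective 7 has no such comparison.

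**Working it through.** **1. The plan's own figures.** The only power statement is for the primary endpoint (Section 12.1.1: at least 1 of 12 to continue, at least 3 of 29 for success, 5% versus 20%). Exact two-stage binomial calculation gives type I error 0.1480, power 0.9005 and early termination 0.95¹² = 0.5404. These agree with the stated 0.15, 0.90 and 0.540. No alpha, power or effect size is given for HR23B.

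**2. Number of responders.** At 5% and 20%, 29 patients give about 1 to 6 responders. Section 8 and Appendix D report 2 partial responses. Section 12.1.1 needs 3 for success.

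**3. What a 2 × 2 table can show (no effect size assumed).** Suppose 2 of 29 respond, both are HR23B-positive, and k tumours are positive. One-sided Fisher p = C(k,2)/C(29,2) = C(k,2)/406.
- k = 6: 15/406 = 0.037
- k = 7: 21/406 = 0.052
- k = 14: 91/406 = 0.22

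So p ≤ 0.05 needs at most 6 of 29 positive. With distinct scores the full score can reach 1/406 = 0.0025. With 3 responders, all positive, p = C(k,3)/3,654: k = 11 gives 165/3,654 = 0.045 and k = 12 gives 220/3,654 = 0.060. At most 11 may be positive.

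**4. How often the odds-ratio interval is unbounded.** My assumptions, not in the documents: n = 29; score normal with SD 3, rounded and limited to 0–13; non-responder mean 3, 4.5 or 6 (20%, 37% or 57% positive); responders 1 SD (3 points) higher. The chance that a responder is positive is q = 1 − Φ((5.5 − mean)/3), which is 0.566, 0.748 or 0.878. With m responders, all fall on one side with probability q^m + (1 − q)^m.
- m = 2: 0.51, 0.62, 0.79
- m = 3: 0.26, 0.43, 0.68
- m = 6: 0.04, 0.18, 0.46

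Simulation, which also counts trials where all non-responders fall on one side, gives these frequencies of an unbounded interval:

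| Responders | Cut at 6 | Full score |
|---|---|---|
| 2 | about 50–80% | about 6–9% |
| 3 | about 27–70% | about 3% |
| 6 | about 4–46% | below 1% |

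**5. Power, if a test were made.** Logistic model linear in the score, 20% response rate, n = 29, two-sided 10% (matching a 90% interval). Entries are power in %, Fisher on the cut → exact Wilcoxon on the full score:

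| Odds ratio per SD | 30% positive | 50% positive | 70% positive |
|---|---|---|---|
| 1.5 | 12→19 | 12→19 | 5→20 |
| 2 | 27→38 | 22→37 | 8→34 |
| 3 | 47→63 | 36→61 | 14→63 |
| 5 | 66→82 | 57→79 | 18→81 |

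At n = 12 the losses are 4–9, 6–14, 8–22 and 11–35 points for the same four odds ratios. In the shift model of step 4 at 0.5 SD (odds ratio per SD about e^0.5 = 1.65), with 2, 3 or 6 responders and a one-sided 5% test, the loss is about 7–18 points. If the truth is a step at 6, the difference is −7 to +9 points at n = 29 and −1 to +8 at n = 12.

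**6. Does the cut cost most in small samples?** The large-sample efficiency of a median cut is φ(0)²/(0.5 × 0.5) = 0.159/0.25 = 0.64. The loss of about 36% does not depend on n. What worsens with few responders is the discreteness shown in steps 3 and 4.

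**The case against.** The plan specifies no HR23B test. Its stated interest is direction, and on that the cut does reasonably well: at a 1 SD shift it points the right way in about 81–96% of simulated trials, against about 89–99% for a comparison of mean scores. Exact logistic regression is only an example of what might follow at Stage 2, so a full-score model is not ruled out. The cut-off is fixed in advance and attributed to a ROC analysis, so applying it in a new tumour is a legitimate check. Part of the power gap is the conservatism of Fisher's test, not the cut. Even the full score has only about 30–32% power with 2 responders at 1 SD (one-sided 5%).

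All of this stands, and it limits the point. A reader might infer that the cut forfeits 20–40 or more points of power, that a real association will usually be missed, or that a small sample is when a cut costs most. The documents support none of these. They state no test or effect size, the size of the loss depends on assumptions, and relative efficiency does not depend on n.

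The objection does not rescue the rationale. A prespecified cut avoids data-driven selection but does not recover the discarded ordering. The interval that the plan itself names as its Stage 2 product is the one most often left unbounded.

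**Conclusion.** The concern holds as a cheap improvement to an exploratory analysis. Small sample size is not a valid reason for the cut, and no full-score analysis is planned. If response rises with the score, the cut costs precision. In the assumed 1 SD scenarios it leaves the odds-ratio interval unbounded in about 50–80% of trials with 2 responders, against about 6–9% for the full score.

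The power loss is a range, not a figure: about zero for a true step at 6 and about 4–18 points for modest effects (odds ratio 1.5–2 per SD with 30–50% positive, or a 0.5 SD shift). At n = 29, losses of 20 or more points in the logistic scenarios needed a strong association (odds ratio about 3 or more per SD) with at least half the tumours positive, or a high positive share (70%) at an odds ratio of 2. Effect size, share positive and shape of the relation are all assumptions.

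No primary or secondary conclusion depends on this. The small number of responders limits the objective more than the cut does.

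**What to change.** In Section 12.4, Exploratory Objective 7:
- Delete sample size as the reason for dichotomizing. If the cut is kept for comparison with the earlier lymphoma work, give that as the reason.
- Add the full score by response: a plot of individual scores, and exact logistic regression with the score as the single predictor (odds ratio per point, 90% interval). An exact Wilcoxon comparison is a rank-based alternative. It is not the same analysis, because it uses ranks, not raw scores, and gives no odds ratio.
- Keep the prespecified ≥6 versus <6 table beside it.
- Reconcile the 0 to 3+ scale in Section 12.4 with the score out of 13 in Appendix D.

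The cost is wording. The score must be determined anyway to apply the cut, and Section 12.4 already names the exact method. Appendix D makes the assays subject to additional funding, but that applies to either analysis. The downside is that a per-point odds ratio assumes a monotone, roughly linear relation. That is uncertain here, because the scoring in Appendix D includes features of skin infiltrate. The plot and the retained table let the reader judge it.
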